- Liver function tests (LFTs; alkaline phosphatase [ALP], gamma-glutamyl transpeptidase [GGT], alanine transaminase [ALT], aspartate transaminase [AST] and

total bilirubin) will be analysed at screening, pre-vaccination on Day 0 and on Days 7, 14, 28, 56, 84 and 168

- HBV disease markers in serum:
 - Healthy participants: qualitative HBsAg will be tested at screening, hepatitis B surface antibody (HBsAb) and HBcAb will be tested at Day 0, and repeated at the end of the trial if negative at baseline, or at discretion of the Investigator
 - CHB participants: HBV DNA and quantitative HBsAg will be tested at screening and repeated on Days 0, 28, 56, 84 and 168. The following parameters will also be analysed on days 0, 28, 56, 84 and 168: HBeAg, HBcAg, anti-HBs, anti-HBe, anti-HBc, pgRNA
- A full physical examination will be performed at screening and pre-vaccination on Day 0. A symptom-directed physical examination will be performed on Days 7, 14, 28, 56, 84 and 168
- Vital signs will be performed at screening, pre-vaccination and post-vaccination at the on Day 0 and on Days 7, 14, 28, 56, 84 and 168
- Local and systemic reactogenicity (pain, induration, warmth, erythema at the vaccination site plus feverishness, chills, myalgia, fatigue, headache, nausea, arthralgia, malaise) will be captured pre-vaccination and post-vaccination on Day 0 and by eDiary for 3 days post-vaccination
- Unsolicited adverse events will be recorded in the eCRF from the date the informed consent is signed, at all clinic visits to cover the period since the previous visit and during the visit and up to 28 days post-vaccination
- Serious adverse events (SAEs) and adverse events of special interest (AESIs) will be recorded from the date the informed consent is signed until the end of the study and or resolved or until participant contact discontinues
- Cellular immune responses will be measured in peripheral blood mononuclear cells (PBMCs) samples taken on pre-vaccination on Day 0 and on Days 14, 28, 56, 84 and 168. Samples will be analysed by ICS

For participants in cohorts 5 and 6, all assessments on Days 0, 7, 14, 28 and 84 above will be performed. In addition, neutralising antibodies to ChadOx1 will be assessed on Days 0 and 84.

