4.2 Inclusion Criteria

Participants must meet *all* the following criteria to be eligible for the study:

1. Adult males or females aged ≥ 18 to ≤ 65 years at screening
2. Body Mass Index $\leq 30 \text{ kg/m}^2$
3. Able to provide informed consent indicating they understand the purpose of, and procedures required, for the study and are willing to participate
4. If female, willing not to become pregnant up to 8 weeks after last dose of study vaccine, not breast feeding
5. If female: Not pregnant and one of the following:
 - Of non-childbearing potential (i.e. women who have had a hysterectomy or tubal ligation or are post-menopausal, as defined by no menses in ≥ 1 year)
 - Sexual abstinence, only if the participant refrains from heterosexual intercourse during the entire study period and it is the usual lifestyle of the participant
 - Of childbearing potential but agrees to practice highly effective contraception for 4 weeks prior to study vaccine and 8 weeks after study vaccine. Highly effective methods of contraception include one or more of the following:
 - Male partner who is sterile (medically effective vasectomy) prior to the female participant's entry into the study and is the sole sexual partner for the female participant
 - Combined (estrogen and progestogen containing) hormonal contraception associated with inhibition of ovulation:
 - oral
 - intravaginal

- transdermal
- Progestogen-only hormonal contraception associated with inhibition of ovulation:
 - oral
 - injectable
 - implantable
 - An intrauterine device
 - Bilateral tubal occlusion

Healthy participants (cohorts 1 and 2):

6. Considered to be healthy with no current conditions that may significantly impair participant safety or influence study results, in the opinion of the Investigator

Participants with well controlled CHB (cohorts 3 and 4):

7. Documented evidence of chronic HBV infection (e.g. HBsAg positive ≥ 6 months with detectable HBsAg levels at screening)
8. Receipt of only either entecavir or tenofovir for at least 12 months before screening
9. Virally suppressed (HBV DNA <40 IU/mL for ≥ 6 months)
10. HBsAg <10000 IU/mL

Healthy participants (cohort 5):

11. Considered to be healthy with no current conditions that may significantly impair participant safety or influence study results, in the opinion of the Investigator
12. Adult males or females aged ≥ 40 to ≤ 60 years at screening
13. Completed second dose of COVID-19 AZD1222 vaccine 10 to 18 weeks before enrolment

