6. STUDY DESIGN

This is a Phase 1, first-in-human study of ChAdOx1-HBV. The study will be conducted in 40 healthy participants and 12 participants with CHB and virally suppressed with oral antiviral medication. This will be an open-label, non-randomised dose escalation study comparing the safety, tolerability and immunogenicity of 2 different doses of ChAdOx1-HBV vaccine. T cell responses in healthy participants who have received a prior two-dose series of AZD1222 will be compared with those who have received at least two doses of the Pfizer mRNA COVID-19 vaccine or the Moderna COVID-19 vaccine. The study design is shown in Figure 1.

Participants will be screened in the period Day -42 to Day -1. Informed consent will be obtained before any study specific procedures are performed. Eligible participants will then attend the clinic to receive study vaccine on Day 0. Participants will be enrolled sequentially.

The study will investigate the study vaccine as shown in Table 1. On Day 0, an electronic diary (eDiary), tape measure and thermometer will be provided to perform self-assessment of local and systemic reactogenicity. All participants will then have a follow-up telephone call on Day 1 and return to the clinic for study assessments on Days 7, 14, 28, 84. Participants in cohorts 1-4 only, will also have follow up visits on Day 56 and Day 168. End of study visit procedures will be performed at the final visit.

Five healthy participants will be administered the low dose first (cohort 1). Dose escalation will only be initiated in the next 5 healthy participants (cohort 2) following Safety Monitoring Committee (SMC) review.

Six CHB participants will be administered the low dose (cohort 3) before the dose escalation is initiated in the remaining 6 CHB participants (cohort 4).

Thirty healthy participants (15 who have received two doses of AZD1222 [cohort 5] and 15 who have received at least two doses of either the Pfizer or Moderna mRNA COVID-19 vaccine [cohort 6]) will be dosed in parallel with the high dose used in cohorts 2 and 4.

The first participant in each of cohorts 1-4 will be assessed for 1 hour in the clinic post-vaccination in case of immediate adverse events (timed after the end of study vaccine administration). All other participants will be assessed for 30 minutes.

Five reviews of the safety, tolerability and available immunogenicity data will be performed by a SMC:

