10.7.2. Secondary Endpoint Analyses

For all immunogenicity data, any results that are <X will be replaced by 0 for summaries.

A multi-parameter index made of CD4+ magnitude, CD4+ avidity, and CD8+ magnitude

The multi-parameter index is made of CD4+ magnitude, CD4+ avidity, and CD8+ magnitude at each scheduled follow-up (Day 28, Day 56, Day 84 and Day 168) using intracellular cytokine staining (ICS) data from a flow cytometer. All ICS data will be background-subtracted and presented in listings. Negative, background-subtracted responses will be set to 0.

Any additional analyses that may be conducted on ICS data will be performed outside of this SAP and described *a priori* within a separate document prepared by Vaccitech.

Mean reduction in HBsAg titre at Day 84 and Day 168 post-vaccination (last visit)

For the CHB participants only (expected number of participants is 12), the reduction in HBsAg titre is derived by subtracting the follow-up \log_{10} -transformed HBsAg from the baseline \log_{10} -transformed HBsAg at each scheduled follow-up (Day 28, Day 56, Day 84 and Day 168). The HBsAg titre and the reduction in the HBsAg titre will be summarised by visit. The summary of HBsAg titres will include the GM and GSD, derived as in Section 10.1.1.

This secondary endpoint specifically references Day 84 (+/- 7 days) and Day 168 (+/- 7 days); other follow-up visits are provided as supportive analyses.

Proportion of CHB participants with HBeAg and HBsAg loss

For the CHB participants only (expected number of participants is 12), loss of HBeAg and HBsAg will be a binary outcome (loss / no loss) and will be provided directly by the Immunology laboratory. Loss will be assessed at each follow-up visit (Day 28, Day 56, Day 84 and Day 168). HBeAg and HBsAg loss will be listed.

Proportion of CHB participants with HBeAg and HBsAg seroconversion

For the CHB participants only (expected number of participants 12), seroconversion of HBeAg and HBsAg is defined as loss of response to the antigen (defined as a value below the limit of detection (i.e. Not detected)) and development of antibody to either HBeAg or surface antigen (HBsAg) (defined as a measurable value above the limit of detection (i.e. Detected)).

The number and percentage of CHB participants meeting the criteria for seroconversion will be summarised. The denominator will be the number of CHB participants in the analysis set with non-missing data.

Reduction of hepatitis B DNA levels

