The denominator is the number of participants with non-missing data at baseline and follow-up.

Table 14.2.3
Reduction in Hepatitis B DNA levels in CHB Participants
Immunogenicity Analysis Set

Hepatitis B DNA (log ₁₀ copies/ml)	Low Dose (N=xx)			High Dose (N=xx)			Total (N=xx)		
	Absolute		Change	Absolute		Change	Absolute		Change
	CHB Participants			CHB Participants			CHB Participants		
Baseline	n	xx		xx	xx		xx	xx	
	Mean	xx, x		xx, x	xx, x		xx, x	xx, x	
	SD	xx, xx		xx, xx	xx, xx		xx, xx	xx, xx	
	Median	xx, x		xx, x	xx, x		xx, x	xx, x	
	Min, Max	xx, xx		xx, xx	xx, xx		xx, xx	xx, xx	
Day 28	n	xx		xx	xx		xx	xx	
	Mean	xx, x		xx, x	xx, x		xx, x	xx, x	
	SD	xx, xx		xx, xx	xx, xx		xx, xx	xx, xx	
	Median	xx, x		xx, x	xx, x		xx, x	xx, x	
	Min, Max	xx, xx		xx, xx	xx, xx		xx, xx	xx, xx	
Day 56	n	xx		xx	xx		xx	xx	
	Mean	xx, x		xx, x	xx, x		xx, x	xx, x	
	SD	xx, xx		xx, xx	xx, xx		xx, xx	xx, xx	
	Median	xx, x		xx, x	xx, x		xx, x	xx, x	
	Min, Max	xx, xx		xx, xx	xx, xx		xx, xx	xx, xx	
Day 84	n	xx		xx	xx		xx	xx	
	Mean	xx, x		xx, x	xx, x		xx, x	xx, x	
	SD	xx, xx		xx, xx	xx, xx		xx, xx	xx, xx	
	Median	xx, x		xx, x	xx, x		xx, x	xx, x	
	Min, Max	xx, xx		xx, xx	xx, xx		xx, xx	xx, xx	
Day 168	n	xx		xx	xx		xx	xx	
	Mean	xx, x		xx, x	xx, x		xx, x	xx, x	
	SD	xx, xx		xx, xx	xx, xx		xx, xx	xx, xx	
	Median	xx, x		xx, x	xx, x		xx, x	xx, x	
	Min, Max	xx, xx		xx, xx	xx, xx		xx, xx	xx, xx	
Maximum Change	n	xx		xx	xx		xx	xx	
	Mean	xx, x		xx, x	xx, x		xx, x	xx, x	
	SD	xx, xx		xx, xx	xx, xx		xx, xx	xx, xx	
	Median	xx, x		xx, x	xx, x		xx, x	xx, x	
	Min, Max	xx, xx		xx, xx	xx, xx		xx, xx	xx, xx	

Change in hepatitis B DNA levels is defined by subtracting the DNA levels at each follow-up visit (Day 28, Day 56, Day 84 and Day 168) from the DNA levels pre vaccination (Day 0). A positive change is equivalent to a reduction in DNA levels.
The denominator is the number of participants in the analysis set.

Programming Note: The data may be provided as copies/ml - this should be transformed to log10 copies/ml before summarising

Table 14.2.4
Background-subtracted T-Cell response (ELISpot)
Immunogenicity Analysis Set

Stimulation Antigen Visit	Healthy Participants						Healthy Participants Covid-19 Vaccinated						Total (N=xx)			
	Low Dose (N=xx)			High Dose (N=xx)			ChAdOx1 (N=xx)			mRNA (N=xx)			Absolute Change		Absolute Change	
	Absolute	Change	Absolute	Absolute	Change	Absolute	Absolute	Change	Absolute	Change	Absolute	Change	Absolute	Change	Absolute	Change

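### HBeAg seroconversion is defined by follow-up status alone, with no requirement that the participant be HBeAg positive and anti-HBe negative at baseline

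*SAP*

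**What the plan says.** **Entry.** Protocol 4.2, criterion 7 asks for "Documented evidence of chronic HBV infection (e.g. HBsAg positive ≥ 6 months with detectable HBsAg levels at screening". The other CHB criteria cover antiviral treatment, HBV DNA suppression and an HBsAg ceiling. Neither the inclusion nor the exclusion criteria mention HBeAg or anti-HBe.

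**Measurement.** Protocol 3.1.2 states: "The following parameters will also be analysed on days 0, 28, 56, 84 and 168: HBeAg, HBcAg, anti-HBs, anti-HBe, anti-HBc, pgRNA". Baseline values of all four markers needed for the two seroconversions therefore exist.

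**Seroconversion, SAP 10.7.2.** The antigen condition is "loss of response to the antigen (defined as a value below the limit of detection (i.e. Not detected". The antibody condition is a detectable antibody to either of the two antigens. "The denominator will be the number of CHB participants in the analysis set with non-missing data".

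**Seroconversion, Table 14.2.2 footnote.** Both antigens must be below the limit of detection and both antibodies at or above it, reported as one combined Yes/No result. "The denominator is the number of participants with non-missing data at baseline and follow-up".

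**Loss, SAP 10.7.2.** Loss "will be a binary outcome (loss / no loss) and will be provided directly by the Immunology laboratory". It is listed, with no table and no denominator.

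**The concern.** Seroconversion is a change of state: antigen present and antibody absent, then the reverse. The SAP words (loss, development) suggest change, but the definitions attached to them describe only what is found at follow-up. The same section computes the HBsAg titre and HBV DNA endpoints explicitly as differences from baseline, so the omission here is noticeable.

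For HBsAg the antigen side does little harm, because entry secures a positive start. For HBeAg nothing does. A participant can satisfy the HBeAg conditions before being vaccinated, or can sit in a denominator where the event cannot happen. In both cases the reported figure depends partly on the baseline HBeAg mix of the CHB cohorts. A reader of Table 14.2.2 could not see how many were at risk: the demography table does not show HBeAg status, and SAP 10.1.8 plans no subgroup analysis.

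**Working it through.** The plan gives no rate, power or event figure for these endpoints, so there is none to reproduce. The only count is the CHB total: 6 low dose + 6 high dose = 12 (SAP 6).

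**1. Apply the two rules to specific participants.**

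- *Participant A* is HBeAg negative, anti-HBe positive, HBsAg positive and anti-HBs negative at baseline, and unchanged at follow-up.
  - SAP 10.7.2 text, read antigen by antigen: HBeAg is not detected and anti-HBe is detected, so A counts as an HBeAg seroconverter.
  - Table 14.2.2: HBsAg is still detected, so A counts as No.
- *Participant B* has the same baseline, but at follow-up HBsAg is not detected and anti-HBs is detected.
  - Table 14.2.2: all four conditions are met, so B counts as Yes for HBeAg and HBsAg seroconversion, although the HBeAg markers never moved.

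**2. Size under the antigen-by-antigen reading.** Let k be the number of the 12 who are HBeAg negative and anti-HBe positive at baseline. The documents do not give k, so a range is shown. Assume the other 12 − k are HBeAg positive and anti-HBe negative, and that no data are missing.

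- Apparent HBeAg seroconversion with no vaccine effect: k/12.
- Highest attainable rate if a change is required but all 12 stay in the denominator: (12 − k)/12.
- Number truly at risk: 12 − k.
- One true event: 1/12 against 1/(12 − k).

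| k (assumed) | No-effect rate k/12 | Ceiling (12 − k)/12 | At risk | One event /12 | One event / at risk |
|---|---|---|---|---|---|
| 4 | 33.3% | 66.7% | 8 | 8.3% | 12.5% |
| 6 | 50.0% | 50.0% | 6 | 8.3% | 16.7% |
| 8 | 66.7% | 33.3% | 4 | 8.3% | 25.0% |
| 10 | 83.3% | 16.7% | 2 | 8.3% | 50.0% |

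**3. Size under the Table 14.2.2 rule.** If nothing changes after baseline, every participant who is still HBsAg positive counts as No, so the table shows 0/12 whatever k is. The k/12 column does not apply. What remains is the mislabelling of participant B.

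**4. Denominators.** The SAP text asks for non-missing data. The table footnote asks for non-missing data at baseline and follow-up. Neither asks for the antigen to be detected at baseline, so neither removes the k participants.

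**The case against.** The strongest reply has four parts.

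- *The wording already means change.* Loss and development imply a starting state, and the table footnote's demand for baseline data suggests a comparison. On this view the bracketed phrases are only assay cut-offs. That is a fair reading of intent. But the footnote writes the rule out as detection limits with no baseline term, and a programmer following it would compare nothing with baseline.
- *The only planned table uses the combined rule.* This stands. A reader might infer from the k/12 column that Table 14.2.2 could show 33% to 83% with no vaccine effect. It could not, because an unchanged participant is HBsAg positive and counts as No. Participant B should also be rare: Protocol 1.2 cites HBsAg loss of 0–3% over up to 52 weeks of nucleotide analogue therapy, and 12 × 0.03 = 0.36 participants at most at that background rate.
- *Loss is a separate matter.* This stands. A reader might infer that HBeAg-negative participants will be recorded as having lost HBeAg. The documents do not show that: the not-detected wording belongs to seroconversion, and the laboratory may apply a baseline condition that is not written down. Loss is only listed, and Listing 16.2.6.2 shows HBeAg and anti-HBe by visit beside the flags.
- *The study is descriptive.* This stands. No formal analysis is planned (SAP 10.1.3), so no error rate or power is affected, and a claim that a 6 versus 6 dose comparison is invalidated would go too far.

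The stated rule and denominators themselves are left unanswered. Under either reading the HBeAg part can be met before vaccination.

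**Conclusion.** The point holds for the seroconversion definition. SAP 10.7.2 and Table 14.2.2 use follow-up status alone, with a denominator that includes participants who cannot have an HBeAg event.

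The consequence depends on which of the two rules is used. Under the SAP text read antigen by antigen, the no-effect HBeAg rate is k/12. Under the table's combined rule, the result is a wrong label for an HBsAg seroconverter who was HBeAg negative from the start. For loss, the absence of a written rule leaves miscounting possible but not demonstrated.

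The conclusion assumes that at least some enrolled CHB participants are HBeAg negative and anti-HBe positive, which the criteria allow but the documents do not quantify. It also assumes that the detectable-HBsAg wording of criterion 7, given there as an example of documentation, is applied to every CHB participant. The endpoint is secondary and descriptive. This should be corrected, but it does not touch the primary safety objective.

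**What to change.** In SAP 10.7.2 and Table 14.2.2:

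1. Report HBeAg seroconversion and HBsAg seroconversion in separate rows.
2. Define each event as antigen detected and antibody not detected at baseline, changing to antigen not detected and antibody detected at follow-up.
3. Use the number of participants who meet the baseline condition as the denominator, and show it for each dose group. If it is zero, state that no participant was at risk instead of giving a percentage.
4. Require the laboratory's loss flag to use the same condition of antigen detected at baseline, and say so in the SAP.

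Separate rows also remove the disagreement between the text (antibody to either antigen) and the footnote (both). The combined seroconversion entry in Listing 16.2.6.2 would be split to match.

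The cost is SAP wording, one table shell, one listing entry and a line in the laboratory specification. No new data are needed, since the Day 0 markers are already collected. The drawback is a small HBeAg denominator, possibly zero. The HBsAg denominator would drop below 12 only for missing data or for anyone with detectable anti-HBs at baseline.

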1.2 Treatment Review

Highly effective prophylactic vaccines were implemented in the early 1980's; however, these vaccines are ineffective once infection is established [2]. Despite the wide use of prophylactic vaccines, there are an estimated 240 million CHB carriers and over 686,000 related deaths per year worldwide [3].

Two classes of antiviral therapies have been approved and recommended for treatment of hepatitis B: interferons (IFNs) and nucleotide analogues (NAs). The use of IFN results in higher rates of hepatitis B e-antigen (HBeAg) and hepatitis B surface antigen (HBsAg) loss compared to NAs.

Pegylated IFN administered for up to 52 weeks results in HBsAg loss in 3-7% of patients compared to 0-3% HBsAg loss after the same duration of NA therapy. Response to IFN is also more durable, and HBsAg loss may occur after cessation of treatment, while virological relapse is frequent after cessation of NA. However, IFN is less effective at suppressing viral replication compared to NAs, requires parenteral administration, is associated with significant side effects, and is contraindicated in patients with decompensated cirrhosis or severe exacerbations of hepatitis and those with autoimmune or psychiatric illnesses.

Nucleotide analogues are administered orally and have negligible adverse effects. The recommended first-line NAs, entecavir and tenofovir, have low risk of drug resistance; but the requirement for indefinite therapy increases the cost and the risk of non-adherence.[4]

Various combinations of IFN and NA have been evaluated, but most studies have not shown an added benefit compared to monotherapy [5,6,7]. A recent study showed that combination of pegylated IFN and tenofovir increased the rate of HBsAg loss to 9.1% at Week 72, but the benefit was mainly observed with those infected with HBV genotype A [8].

Many research programs are ongoing to develop new treatment concepts that focus on the clearance of HBsAg in a significant proportion of patients, with the principle aims of: 1) stopping treatment with no risk of virological relapse and no risk of liver disease progression and, 2) to further decrease the risk of HCC. Several potential target mechanisms for immune modulation to restore HBV specific immune responses in conjunction with profound inhibition of HBV replication and HBsAg production to attain immunological control are being evaluated [3].

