All medications are coded using the WHO Drug Dictionary, Global Version (September 2019).
Concomitant medications correspond to medications where the stop date is not before the vaccination date.
The table shows distinct number of participants with each WHO Drug name/Drug Class.
Percentages are based on the safety analysis set.
All COVID-19 vaccinated participants were given the high dose of ChAdOx1-HBV vaccine.

Table 14.2.1
Reduction in HBsAg titre post-vaccination in CHB participants
Immunogenicity Analysis Set

HBsAg (IU/mL)	CHB Participants					
	Low Dose (N=xxx)		High Dose (N=xxx)		Total (N=xxx)	
	Absolute	Change	Absolute	Change	Absolute	Change
Baseline	n	XX	XX	XX	XX	XX
	GM	XX.X	XX.X	XX.X	XX.X	XX.X
	GSD	XX.XX	XX.XX	XX.XX	XX.XX	XX.XX
	Median	XX.X	XX.X	XX.X	XX.X	XX.X
	Min, Max	XX, XX	XX, XX	XX, XX	XX, XX	XX, XX
Day 28	n	XX	XX	XX	XX	XX
	GM	XX.X	XX.X	XX.X	XX.X	XX.X
	GSD	XX.XX	XX.XX	XX.XX	XX.XX	XX.XX
	Median	XX.X	XX.X	XX.X	XX.X	XX.X
	Min, Max	XX, XX	XX, XX	XX, XX	XX, XX	XX, XX
Day 56	n	XX	XX	XX	XX	XX
	GM	XX.X	XX.X	XX.X	XX.X	XX.X
	GSD	XX.XX	XX.XX	XX.XX	XX.XX	XX.XX
	Median	XX.X	XX.X	XX.X	XX.X	XX.X
	Min, Max	XX, XX	XX, XX	XX, XX	XX, XX	XX, XX
Day 84 [1]	n	XX	XX	XX	XX	XX
	GM	XX.X	XX.X	XX.X	XX.X	XX.X
	GSD	XX.XX	XX.XX	XX.XX	XX.XX	XX.XX
	Median	XX.X	XX.X	XX.X	XX.X	XX.X
	Min, Max	XX, XX	XX, XX	XX, XX	XX, XX	XX, XX
Day 168 [1]	n	XX	XX	XX	XX	XX
	GM	XX.X	XX.X	XX.X	XX.X	XX.X
	GSD	XX.XX	XX.XX	XX.XX	XX.XX	XX.XX
	Median	XX.X	XX.X	XX.X	XX.X	XX.X
	Min, Max	XX, XX	XX, XX	XX, XX	XX, XX	XX, XX

GM = antilog(mean(log(HbsAg))), GSD = antilog(sdi(log(HbsAg)))

A summary of the change is obtained by summarising the difference in the log-transformed results ($\log(\text{HbsAg at baseline}) - \log(\text{HbsAg at follow-up})$) and back-transforming. The mean change is then the GM ratio, where a GM ratio > 1 is equivalent to a reduction in HbsAg.

[1] Visits at Day 84 and Day 168 are the protocol defined secondary endpoints of the study.

Table 14.2.2
Proportion of CHB participants with HBeAg and HBsAg Seroconversion
Immunogenicity Analysis Set

	HBeAg and HBsAg Seroconversion	CHB Participants		
		Low Dose (N=xx)	High Dose (N=xx)	Total (N=xx)
Yes	n (%)	xx (xx.x)	xx (xx.x)	xx (xx.x)
No	n (%)	xx (xx.x)	xx (xx.x)	xx (xx.x)

Seroconversion is defined as the loss of response to the antigen HbeAg and HbsAg and the development of antibody to HbeAg and HbsAg (i.e. [HbeAg and HbAg < LLOD] and [anti-HBs and anti-Hbe ≥ LLOD]).

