				Nausea	ddmmyy	xx.x	yes/no	xx.x	xx.x	yes/no	xx.x	xx.x	xx.x	xx.x
				Feverishness	ddmmyy	xx.x	yes/no	xx.x	xx.x	yes/no	xx.x	xx.x	xx.x	xx.x
				Chills	ddmmyy	xx.x	yes/no	xx.x	xx.x	yes/no	xx.x	xx.x	xx.x	xx.x
				Joint ache	ddmmyy	xx.x	yes/no	xx.x	xx.x	yes/no	xx.x	xx.x	xx.x	xx.x
				Generally feeling unwell	ddmmyy	xx.x	yes/no	xx.x	xx.x	yes/no	xx.x	xx.x	xx.x	xx.x
				Medication Taken	ddmmyy	xx.x	yes/no	xx.x	xx.x	yes/no	xx.x	xx.x	xx.x	xx.x
				Visit to A&E	ddmmyy	xx.x	yes/no	xx.x	xx.x	yes/no	xx.x	xx.x	xx.x	xx.x

* = indicates worst post-baseline incidence/highest value
All local and systemic reactions recorded on Day 0 (pre and post) are as recorded by the investigator. The reactions recorded Day 1 to day 3 are recorded by the participant in a diary card.

Severity: 0 = None, 1 = No interference with daily activities, 2 = Some interference with daily activities, 3 = Significant interference with daily activities, 4 = ER visit or hospitalization.
Medication Taken and Visit to A&E are yes if these were recorded as such for any symptom at the specific timepoint.

Programming note: place a "*" against the worst post-baseline incidence/highest value for each reaction for each participant, in the event of a tie the first one should be flagged. If all 0 then none should be flagged
Programming note: The numeric grade should be displayed in the listing

Listing 16.2.6.1.2
Diary Card: Medications Taken

Cohort	Participant	Study Day	Date/time	Symptom(s)	Medication Taken	Medication Name	Dose taken (units)	Number of times taken	Additional symptoms this medication refers to
xxxxxx	xxxxxx	0/1/2/3	ddmmmyyy hh:mm	xxxxxx	xxxxxx	xxxxxx	xxxx	xx	xxxxx

Programming Note: Only display details for the days on which medication was taken. If no medication taken throughout then this listing will be empty
Programming Note: Symptoms should list all of the symptoms that this medication was listed against on the specific day it was taken.

Listing 16.2.6.2
HBV Disease Markers

Cohort	Participant	Visit	Date/time	Parameter	Result	Comments
xxxxxx	xxxxxx	Day x	ddmmyyy / hh:mm	HBV DNA HBV pRNA Hepatitis B surface Antibody Hepatitis B surface Antigen Hepatitis B core Antibody Hepatitis B core Antigen Hepatitis B e Antibody Hepatitis B e Antigen		

Multi-parameter index
HBeAg loss
HBsAg Loss
HbeAg and HBsAg seroconversion

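### SAP 10.7.2 and Table 14.2.2 define seroconversion differently, so the table can hide a single-marker seroconversion; the HBeAg/HBsAg loss proportion has no summary

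*SAP*

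**What the plan says.** **Text.** SAP 10.7.2 defines seroconversion of HBeAg and HBsAg as loss of response to 'the antigen' (singular, below the limit of detection) together with "development of antibody to either HBeAg or surface antigen (HBsAg) (defined as a measurable value above the limit of detection (i.e. Detected".

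**Table shell.** The footnote to Table 14.2.2 says: "Seroconversion is defined as the loss of response to the antigen HbeAg and HbsAg and the development of antibody to HbeAg and HbsAg". It then gives the operative rule: "HbeAg and HbAg < LLOD] and [anti-HBs and anti-Hbe ≥ LLOD". The shell has one combined item with a Yes row and a No row, by dose group. It has no rows by marker or by visit. Its denominator note reads: "The denominator is the number of participants with non-missing data at baseline and follow-up".

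**Listing.** Listing 16.2.6.2 carries the derived parameter "HbeAg and HBsAg seroconversion" as one item, although it has separate items for HBeAg loss and HBsAg loss.

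**Baseline.** Protocol 4.2 asks for "Documented evidence of chronic HBV infection (e.g. HBsAg positive" as an example of proof of infection, and also requires viral suppression and an upper limit on HBsAg. It sets no HBeAg status for the CHB cohorts. The Day 0 markers are collected (Protocol 3.1.2): "The following parameters will also be analysed on days 0, 28, 56, 84 and 168: HBeAg, HBcAg, anti-HBs, anti-HBe, anti-HBc, pgRNA".

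**Loss.** SAP 7.2 and Protocol 10.2.2.5 state HBeAg/HBsAg loss as a proportion. SAP 10.7.2 says that the laboratory supplies it as a binary outcome and that it will be listed. SAP 13.2 has no table for it, and SAP section 11 does not name this as a change from the protocol.

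**The concern.** 'Either' in the text and 'and' in the footnote are different rules, and the reported seroconversion proportion depends on which one is programmed. The footnote's rule is the most restrictive possible. A reader of the study report who sees 0/12 in Table 14.2.2 would take it to mean that nobody seroconverted, when a participant may have seroconverted for one of the two markers.

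There is a fault in the other direction too. 'Loss' and 'development' describe a change, but the thresholds in both places refer only to the follow-up result. Because entry does not depend on HBeAg status, some participants may already meet the HBeAg conditions on Day 0.

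The loss endpoint raises a simpler question: the protocol plans a proportion, and the SAP produces none and does not say so.

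**Working it through.** The documents give no rate or sample-size figure for this endpoint, so the check compares the rules over every possible follow-up result.

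**Inputs.** Four binary markers at follow-up: HBeAg lost (e), anti-HBe detected (ae), HBsAg lost (s), anti-HBs detected (as). That gives 2^4 = 16 states. I take 'HbAg' in the footnote to mean HBsAg.

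**Rules.**

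- Table 14.2.2: e and ae and s and as. 'Yes' in 1 state.
- Text, reading A (an antigen lost with its own antibody, for either marker): (e and ae) or (s and as). 4 + 4 − 1 = 7 states.
- Text, reading B (both antigens lost, either antibody): e and s and (ae or as). 3 states.
- Text, reading C (any antigen lost, either antibody): (e or s) and (ae or as). 3 × 3 = 9 states.

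The table's single 'Yes' state is 'Yes' under A, B and C, so the disagreements are 7 − 1 = 6, 3 − 1 = 2 and 9 − 1 = 8 states.

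**Selected states.**

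| Follow-up state | Table | A | B | C |
|---|---|---|---|---|
| HBeAg lost, anti-HBe present; HBsAg persists, no anti-HBs | No | Yes | No | Yes |
| HBsAg lost, anti-HBs present; HBeAg persists, no anti-HBe | No | Yes | No | Yes |
| Both antigens lost, anti-HBs only | No | Yes | Yes | Yes |
| Both antigens lost, anti-HBe only | No | Yes | Yes | Yes |
| Both antigens lost, both antibodies | Yes | Yes | Yes | Yes |

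An HBeAg-only seroconversion is 'No' in the table whatever the anti-HBs result. It is 'Yes' under A and C and 'No' under B. HBsAg seroconversion without detectable anti-HBe is also always 'No' in the table. Where HBeAg is undetected as well, that case is 'Yes' under all three readings.

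**Baseline.** Take a participant who is HBeAg-negative and anti-HBe-positive on Day 0 and unchanged at follow-up. Then e and ae both score as met, since only follow-up status is tested. Under A or C that participant is 'Yes' with no change at all. In the table, the HBeAg half is satisfied without change and the result rests on HBsAg alone.

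**Size.** One reclassified participant is 1/6 = 16.7 percentage points of a dose cohort, or 1/12 = 8.3 points of all CHB participants.

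**The case against.** The strongest reply is that the endpoint is worded with 'and' throughout, so the text could define seroconversion marker by marker and then require it for both. That gives the table's rule exactly. A reader might infer that no reading of SAP 10.7.2 fits the table. That goes too far: this conjunctive reading does fit, though it strains the word 'either'. It is also weakened by Listing 16.2.6.2, which treats the same 'and' as two separate items when the subject is loss.

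Next, SAP 10.1.2 sends the programmer to Section 14 for the format and content of each presentation, and to the table templates for denominators. That points towards the shell. It is not a precedence rule for endpoint definitions, and if the shell is followed, the restrictive version is what gets reported.

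For loss, SAP 10.1.2 says in general that categorical variables are summarised by counts and percentages. The specific instruction to list loss, and the absence of a table, stand against that. SAP section 4 promises that deviations will be described in the study report. That helps with disclosure but does not say which definition is the plan.

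Finally, there is no formal testing (SAP 10.1.3), and Listing 16.2.6.2 shows every marker, and each antigen loss separately, by participant and visit. Any proportion can be counted by hand. This stands, and it limits the harm.

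**Conclusion.** The point holds as a minor inconsistency in planned reporting. The text and the table state different antibody conditions, the text leaves the antigen condition open, and the table's rule can conceal a single-marker seroconversion. The loss proportion has no planned summary and no declaration. The primary safety objective and data collection are not affected.

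The state counts (1 against 3, 7 or 9) are logical cases, not a misclassification rate. The documents give no rate of HBeAg seroconversion, so the frequency of the HBeAg-only case is unknown.

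Two stronger conclusions that a reader might draw are not supported:

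- That a participant who is HBeAg-negative at baseline can never be 'Yes' in the table. This would follow only if the rule tested change. The footnote tests follow-up status, so such a participant with anti-HBe who seroconverts for HBsAg is 'Yes'.
- That the protocol's background rate measures the problem. Protocol 1.2 says that pegylated interferon for up to 52 weeks "results in HBsAg loss in 3-7% of patients compared to 0-3% HBsAg loss after the same duration of NA therapy". At 3%, none of 12 would lose HBsAg with probability 0.97^12 = 69.4%, and the row would then be 0/12. But that figure estimates how often HBsAg loss occurs, not how often text and table disagree. Moreover, these participants have already had at least 12 months of entecavir or tenofovir, follow-up is 24 weeks, and the vaccine's effect is unknown.

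**What to change.** 1. Use one definition of seroconversion in SAP 10.7.2, the Table 14.2.2 footnotes and Listing 16.2.6.2.
2. In Table 14.2.2, report HBeAg seroconversion and HBsAg seroconversion as separate n/N rows by dose group at stated visits, each defined as the antigen lost with its own antibody detected. The combined row can stay if it is wanted.
3. For each marker, show the number with the antigen detected at baseline as a denominator, from the Day 0 data already collected, alongside the all-CHB denominator that the plan uses. There is no need to exclude participants who already have the matching antibody at baseline; nothing in the documents calls for that restriction.
4. Add n/N rows for HBeAg loss and HBsAg loss, or declare in SAP section 11 that loss is listed only.

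The cost is SAP wording and one revised table, with no new data. The drawback is that the HBeAg denominators may be very small within a cohort of 6, which n/N reporting makes plain.
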